7.5.5.7 Adverse Events

All AEs will be recorded from the time the subject signs the informed consent through 30 days following the last administration of study drug. Assessments of AEs will occur at each study visit (phone and clinic). At each visit subjects will be asked about any new or ongoing AEs since the previous visit. The determination, evaluation, reporting, and follow-up of AEs will be performed as outlined in Section 8.5.

Clinically significant changes from Baseline in physical examination findings, vital signs, weight, and clinical laboratory parameters will be recorded as AEs or SAEs, if appropriate.

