8.5.4 Adverse Event Reporting

8.5.4.1 General

All AEs (i.e. any new or worsening in severity or frequency of a preexisting condition) with onset after the subject signs consent for study participation must be promptly documented on the CRF. The Investigator is responsible for evaluating all AEs, obtaining supporting documents, and ensuring documentation of the event is adequate. Details of the AE must include severity, relationship to study drug, duration, and outcome.

All AEs will be collected from the time the subject signs informed consent through 30 days following the last dose of study drug. In addition, the Investigator should report any AE that occurs after this time period that is believed to have a reasonable possibility of being associated with study drug.

AEs ongoing at 30 days following the last dose of study drug should have a comment in the source document by the Investigator whether the event has recovered, recovered with sequelae, or stabilized.

8.5.4.2 Serious Adverse Events, Serious Adverse Drug Reactions, and Requirements for Immediate Reporting

Ultragenyx or its designee must be notified of any SAE that occurs at any time during the reporting period within 24 hours of the Investigator, designee, or site personnel's knowledge of the event. SAEs will be reported by completing and submitting SAE report forms to Ultragenyx or its designee.

Follow-up SAE information must be submitted in a timely manner as additional information becomes available. All SAEs regardless of relationship to study drug must be followed to resolution or stabilization if improvement is not expected.

All deaths, regardless of causality, occurring from the signing of the informed consent until 30 days following the last dose of study drug are to be reported as SAEs to Ultragenyx or its designee within 24 hours of knowledge.

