5.15 Total Duration of UX007 Exposure

For each subject, the total duration of UX007 exposure is defined as sum of duration in the UX007 treatment regimen log. For each analysis, the total duration will be calculated up to last visit date as of the specified clinical cutoff date or the early termination/study completion date, whichever is earlier.

5.16 % of Daily Caloric Intake Provided by Prescribed UX007 Dose

For each subject, an overall average percent of daily caloric intake provided by prescribed UX007 dose will be derived using the UX007 treatment log based on the following rules:

- Percent of daily caloric intake provided by prescribed UX007 dose will be as entered in that entry of the UX007 treatment regimen log for the duration between the start and stop dates when a single log entry has no duplicates with same start and stop date.

- For multiple log entries with same start date and same stop date, the total percent of daily caloric intake is the sum of percent of daily caloric intake of those log entries for that duration.
- Duration is defined as stop date – start date + 1 for each entry in the UX007 treatment log. If a treatment log has a stop date after the specified clinical cutoff date, the duration will be calculated as clinical cutoff date – start date + 1 for each entry in the UX007 treatment log .

Overall average percent of daily caloric intake = Sum of (percent of daily caloric intake * duration) / Sum of duration in the UX007 treatment regimen log.

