5.21 Exposure-adjusted Adverse Event Incidence Rate

The exposure-adjusted adverse event incidence rate is defined as the total number of occurrences of an AE summed across all subjects in the group divided by the total observation time for AEs for subjects in that group. The observation time for each subject is the duration from study day 1 (i.e., first dose of UX007) till the end of study period 1 or the date of clinical cutoff, whichever occurs earlier. The total observation time for AEs is the sum of observation times for all subjects in that group.

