7.2.3 Missing Date Imputation for Adverse Events and Concomitant Medications

The following conventions will be used to impute missing portions of dates for adverse events and concomitant medications. Note that the imputed values outlined here may not always provide the most conservative date.

Missing Start Dates

- If the day is unknown, then:
 - If the month and year match the first dose of investigational product start date month and year in this study, then impute the day of the first dose date.
 - Otherwise, assign the first day of the month.
- If the month is unknown, then:
 - If the year matches the year of the first dose of investigational product date in this study, then impute the month and day of the first dose date in this study.
 - Otherwise, assign 'January'
- If the year is unknown, then the date will not be imputed and will be assigned a missing value.

If the imputed date is earlier than birth date, then birth date will be used. If the imputed start date is later than the end date, then the start date will be set as the same date as the end date.

Missing Stop Dates (not applicable to ongoing)

- If the day is unknown, then assign the last day of the month.
- If the month is unknown, then assign 'December.'
- If the year is unknown, then the date will not be imputed and will be assigned a missing value, and the event will be considered ongoing. If the AE has been recorded as resolved/recovered, all efforts should be made to obtain the date from the Investigator.
- If the resulting end date is after the date of study completion / discontinuation/ data cutoff, set the imputed end date as close to the date of study completion / discontinuation/ data cutoff as possible without overwritten existing information.

If the year is missing for the start date and the stop date (observed or imputed) is on or after the first dose or event is ongoing, the start date will be imputed as the first dose date.

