8 STATISTICAL METHODS OF ANALYSES

8.1 General Principles

This statistical analyses are mostly descriptive analyses with statistical tests performed for select. All statistical tests will be two-sided and tested at statistical significant level of 0.05. The statistical analyses will be reported using summary tables, figures, and data listings. Continuous variables will be summarized by number of subjects and mean, standard deviation (SD), median, minimum, and maximum values. Categorical variables will be summarized by number and percentage of subjects. All raw data obtained from the CRFs will be included in data listings

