8.7.1.1 Gastrointestinal Adverse Drug Reactions

Summaries of gastrointestinal adverse drug reactions (GI ADRs) will be prepared to within each cohort. GI ADRs include the following PTs: Diarrhea, Abdominal pain, Abdominal pain upper, Gastrointestinal pain, Abdominal discomfort, Abdominal distension, Vomiting, and Nausea.

Summaries to characterize the severity and outcome of GI ADRs will include the following:

- 1) incidence of subjects with at least one GI ADR,
- 2) incidence of GI ADRs leading to treatment discontinuation,
- 3) a frequency distribution of the number of GI ADRs per subject,
- 4) descriptive statistics (n, mean, standard deviation, standard error, median and first and 3rd quartiles) for the number of GI ADRs per subject,
- 5) the frequency GI ADRs by severity and seriousness grade
- 6) a frequency distribution of the outcome of the GI ADRs that were
 - a) Recovered/Resolved
 - b) Resolving/Recovering
 - c) Recovered/Resolved with Sequelae
 - d) Death
 - e) Not Resolved

Characterization of the time course of GI ADRs will be provided for:

- 1) Time to first GI ADR with
- 2) Frequency of GI ADRs by time categories
- 3) Number of Subjects with GI ADR by time categories
- 4) descriptive statistics by time categories for any GI ADR

The frequency distributions will the following categories: <= 8 Weeks, > 8 Weeks to <= 24 Weeks, > 24 Weeks to <= 48 Weeks, > 48 Weeks to <= 78 Weeks, > 78 Weeks to <= 102 Weeks, > 102 Weeks to <= 126 Weeks, > 126 Weeks to <= 150 Weeks, > 150 Weeks to <= 198 Weeks, > 198 Weeks to <= 222 Weeks, etc.

The duration of a treatment-emergent GI ADR that was resolved is defined as AE end date minus AE start date plus 1 day. The duration of a treatment-emergent GI ADR for GI events

that are ongoing is defined as data cutoff date minus AE start date plus 1 day. The duration of treatment-emergent GI ADRs will be categorized as follows: 1 Day, 2 to <= 3 Days, 4 to <= 7 Days, 8 to <= 14 Days, 15 to <= 28 Days, and > 28 Days. Descriptive statistics will be also be provided.

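### Ongoing GI adverse drug reactions are timed to the data cutoff even after the subject has left, which can inflate the mean, SD and maximum duration

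*SAP*

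**What the plan says.** SAP 8.7.1.1 has two duration rules. A resolved GI ADR runs from start date to end date, plus one day. For events "that are ongoing is defined as data cutoff date minus AE start date plus 1 day", nothing refers to when the subject left. Durations from both rules go into six bands, the highest being over 28 days, and into descriptive statistics. The section does not list those statistics for duration. The default in SAP 8.1 for a continuous variable is number of subjects with "mean, standard deviation (SD), median, minimum, and maximum values".

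Other durations in the SAP stop at exit:

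- Total exposure (5.15) is counted up to the last visit as of the "clinical cutoff date or the early termination/study completion date, whichever is earlier".
- AE observation time (5.21) runs from study day 1 "till the end of study period 1 or the date of clinical cutoff, whichever occurs earlier". Under 5.10.1, study period 1 ends at the subject's last visit, and the safety follow-up is one of the dates considered.
- The Kaplan-Meier curves for time to first GI ADR, also in 8.7.1.1, are censored at the earlier of end of study and cutoff.

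SAP 7.2.3 pulls imputed stop dates back to study exit, but under the heading "Missing Stop Dates (not applicable to ongoing", so ongoing events are excluded. A stop date with an unknown year makes the event ongoing. For that case the SAP adds: "If the AE has been recorded as resolved/recovered, all efforts should be made to obtain the date from the Investigator".

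On collection, Protocol 7.5.5.7 records AEs "through 30 days following the last administration of study drug". Protocol 8.5.4.1 adds that "AEs ongoing at 30 days following the last dose of study drug should have a comment in the source document" on whether they have recovered, recovered with sequelae or stabilised.

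**The concern.** For a subject still on study at a snapshot, the cutoff is close to the last observation and the rule does little harm. For a subject who left earlier with a GI ADR recorded as ongoing, it counts the whole interval from exit to cutoff as time with the event. Routine collection has stopped by then, so most of that interval is unobserved. An event can then be reported as lasting longer than the period in which the SAP regards that subject as under AE observation.

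The situation is foreseeable. The plan tabulates GI ADRs leading to treatment discontinuation and has outcome categories for events that are resolving or not resolved. Subjects who stop because of a GI event are the ones most likely to leave with it open. Participation can last 84 months, so a gap of years between an early exit and a late cutoff is possible.

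GI events are the listed adverse drug reactions in Protocol 5.3, and the SAP's summary of changes says these tables were added to describe their severity, outcome and time course. A mean of weeks or a maximum of years built from unobserved time would misdescribe them.

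**Working it through.** The plan gives no GI ADR duration, event count or cutoff date for this study, so there is no figure of its own to reproduce. The check compares the stated rule with one capped at exit.

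**Inputs.** From the documents: the ongoing rule (SAP 8.7.1.1), AE collection to 30 days after last dose (Protocol 7.5.5.7), the safety call at 30–35 days (Protocol 7.5.1), and 3 days as the median duration of the most frequent GI events in earlier UX007 trials (Protocol 5.3). Assumed: 41 events, 40 of them exactly 3 days and one unresolved, and gaps g of 1, 3 or 4 years.

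**Formulas.** The excess for one event is cutoff minus exit. If the single unresolved event has duration x:

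- mean = (40 × 3 + x) / 41
- SD = (x − 3) / √41, with √41 = 6.403

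**Case A: the event had lasted 10 days at exit, and there was no later contact.** Uncapped, x = 10 + 365.25 g.

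| Rule | x (days) | Mean | SD | Maximum |
|---|---|---|---|---|
| Capped at exit | 10 | 130/41 = 3.2 | 7/6.403 = 1.1 | 10 |
| To cutoff, g = 1 | 375.25 | 495.25/41 = 12.1 | 372.25/6.403 = 58 | 375 |
| To cutoff, g = 3 | 1,105.75 | 1,225.75/41 = 29.9 | 1,102.75/6.403 = 172 | 1,106 |
| To cutoff, g = 4 | 1,471 | 1,591/41 = 38.8 | 1,468/6.403 = 229 | 1,471 |

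The count over 28 days goes from 0 to 1 of 41.

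**Case B: onset 10 days before last dose, still unresolved at a safety call 30 days after last dose.** Capped at the call, x = 10 + 30 + 1 = 41.

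| Rule | x (days) | Mean | SD | Maximum |
|---|---|---|---|---|
| Capped at the call | 41 | 161/41 = 3.9 | 38/6.403 = 5.9 | 41 |
| To cutoff 3 years after the call | 1,136.75 | 1,256.75/41 = 30.7 | 1,133.75/6.403 = 177 | 1,137 |

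The count over 28 days is 1 of 41 under both rules. An event that began on treatment and is unresolved at the call has already lasted at least 30 + 1 = 31 days.

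The median is 3 days in every row of both tables.

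**A second illustration with natural spread.** Take 100 events at lognormal quantiles with median 3 days and log-SD 1.0 (assumed). Two of them are ongoing after 14 days at exit, and the cutoff is 1,096 days later. Capped: mean 5.1, SD 5.8, maximum 39. To cutoff: mean 27.0, SD 155.6, maximum 1,110. The rise in the mean is 2 × 1,096 / 100 = 21.9 days. The count over 28 days goes from 1 to 3, and the median stays at 3.0.

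**The case against.** The main objection is that little depends on this. It is a descriptive summary with no test behind it. The top band absorbs very long values, the median is robust, and a 1,000-day duration would be visible and traceable in the listings. This stands, and it limits how much weight the point deserves.

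Second, the error runs against the drug: it lengthens reported GI events and cannot hide harm. That is true, but the number is still wrong. It also follows that a capped duration is only a lower bound, so a cap alone is not the full answer.

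Third, affected events may be rare. The safety call is made even if the early termination visit is missed. Protocol 7.3.3 asks for clinically meaningful abnormalities to be followed until they resolve or are judged unlikely to. Protocol 7.5.1 lets follow-up continue at the investigator's judgement, and SAP 7.2.3 asks for missing dates of resolved events. These provisions reduce the number of affected events but do not bound the derivation; an event judged stable may never receive an end date. They do make Case A mainly a loss-to-follow-up case, and Case B the more usual one.

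Fourth, setting 40 events at exactly 3 days makes the capped SD unnaturally small. That is fair, but the lognormal illustration shows the same inflation from a capped SD of 5.8.

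Last, exposure and observation time are subject-level quantities, and the dosing-log durations in SAP 5.16–5.18 truncate only at the cutoff. Those log entries carry their own stop dates, however. The closest comparator, the Kaplan-Meier censoring in the same section, does use the earlier date.

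**Conclusion.** The concern holds. Followed as written, SAP 8.7.1.1 counts time after a subject has left as duration of a GI ADR, and no other section supplies the missing cap. A single affected event can dominate the mean, SD and maximum. In the illustrations with a three-year gap, the mean rises from between 3 and 5 days to between 27 and 31 days, and the SD rises to between 156 and 177. These sizes rest on assumed event counts, durations and gaps. The number of subjects who will leave with an open GI ADR is not in the documents; if there are none, there is no effect. The median moves little when few events are unresolved. The count over 28 days is also little affected, except for short events with no contact after exit. No efficacy result or statistical test is touched. This should be corrected, but it does not threaten the study's main conclusions.

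**What to change.** In SAP 8.7.1.1, end an ongoing GI ADR at the earlier of the data cutoff and the subject's last AE contact. Define that contact as the safety follow-up call, the early termination or completion visit, or later documented follow-up. The end of study period 1 in 5.10.1 already gives most of this date.

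Because the capped value is a lower bound, then do one of two things:

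- treat ongoing events as right-censored and report the Kaplan-Meier median and quartiles of duration; or
- summarise ongoing events separately from resolved ones.

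The second is simpler and is enough. Show events recorded as resolved whose stop year is still unknown after query on their own line, not as ongoing. This needs a stated exception to 7.2.3 for this table.

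The cost is a short wording change with the date definition and that exception, one derivation and one table. No new data are needed.

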8.7.2 Clinical Laboratory Parameters

8.7.2.1 Biomarkers & LC-FAOD Laboratory Measures

Biomarkers and relevant indicators of LC-FAOD are summarized in [Table 8.7.1](#). Blood samples will be collected at each clinic visit to assess relevant biomarkers and laboratory measures of LC-FAOD.

Table 8.7.1: Biomarkers and LC-FAOD-related Laboratory Measures

Biomarkers of UX007 Effects	LC-FAOD Laboratory Measures
Skeletal myopathy biomarkers: serum creatine kinase (CK)	Total and free plasma carnitine
Hepatic disease biomarkers: serum glucose, serum liver enzymes (ALT, AST, GGT)	Plasma acylcarnitines Urine organic acids

Descriptive statistics for clinical laboratory values (in SI units) and changes from the baseline values at each scheduled visit will be presented for the following laboratory parameters:

- Total and free plasma carnitine
- Plasma acylcarnitines
- Urine organic acids

Shift tables pairing each subject's baseline severity grade with the subject's highest post-baseline severity grade will be presented for the following parameters:

- Fasting serum glucose
- Triglycerides

- Creatine kinase (CK)
- Alanine aminotransferase (ALT)
- Aspartate aminotransferase (AST)
- Gamma glutamyl transpeptidase (GGT)

8.7.2.2 Clinical Laboratory Tests

Clinical laboratory values (in SI units) at each visit will be presented for the following laboratory parameters as listed in the following table:

Table 8.7.2: Clinical Laboratory Assessments

Chemistry	Hematology	Urinalysis
Alanine aminotransferase (ALT) ¹	Hematocrit	Appearance
Alkaline phosphatase	Hemoglobin	Color
Aspartate aminotransferase (AST) ¹	MCH concentration (MCHC)	pH
Bilirubin (total)	Mean corpuscular hemoglobin (MCH)	Specific gravity
Blood urea nitrogen (BUN)	Mean corpuscular volume (MCV)	Ketones
Chloride	Platelet count	Protein
Cholesterol (total)	Red blood cell (RBC) count	Glucose
Serum creatinine	Reticulocyte count	Bilirubin
Gamma-glutamyl transpeptidase (GGT) ¹	WBC differential	Nitrite
Serum glucose, fasting ¹	Neutrophil count (absolute and %)	Urobilinogen
Lactate dehydrogenase (LDH)	Lymphocyte count (absolute and %)	Blood
Potassium	Monocyte count (absolute and %)	Creatinine
Protein (albumin and total)	Eosinophil count (absolute and %)	
Sodium	Basophil count (absolute and %)	
	White blood cell (WBC) count	

The frequency and percentage of subjects who experience abnormal clinical laboratory results (i.e. outside of reference ranges) and/or clinically significant abnormalities will be presented.

All valid assessments will be converted into SI units. In calculating change from baseline at each scheduled visit, only subjects with non-missing values at both baseline and the individual scheduled visit are included. All available data (i.e., scheduled and unscheduled assessments) are, however, used in identifying abnormalities in shift tables. Severity for the selected clinical laboratory parameters will be graded according to Common Terminology Criteria for Adverse Events (CTCAE) version 5.0. CTCAE severity grades for selected laboratory parameters are listed in Appendix 11.

Hy's Law criteria will be applied against test results. Subjects with serum total bilirubin $>2 \times \text{ULN}$ and ALT or AST $>3 \times \text{ULN}$ will be identified and further reviewed to confirm there is no other reason to explain the lab increases before confirming Hy's law status. Results will be presented in shift tables. For Hy's Law, shift tables will be produced:

- Hy's Law negative at baseline, remaining Hy's Law negative throughout the study
- Hy's Law negative at baseline, becoming Hy's Law positive at any point during the study
- Hy's Law positive at baseline and Hy's Law negative throughout the study
- Hy's Law positive at baseline and Hy's Law positive at any point during the study

A data listing of all subjects who are Hy's Law positive will be produced.

Potential liver / muscle damage will be assessed based on clinical laboratory test results (and to differentiate it from possible muscle degradation) based on AST, ALT, GGT and CK test results shown below. All results will be listed, and subjects identified with potential toxicity stemming from liver, muscle or both will be flagged.

Table 8.7.3: Screen for Liver/Muscle Damage

AST and ALT	GGT $\leq 1.5 \times \text{ULN}$		GGT $> 1.5 \times \text{ULN}$	
	CK $\leq \text{ULN}$	CK $> \text{ULN}$	CK $\leq \text{ULN}$	CK $> \text{ULN}$
Both $\leq 1.5 \times \text{ULN}$	No Toxicity Flag	No Toxicity Flag	No Toxicity Flag	No Toxicity Flag
Either $> 1.5 \times \text{ULN}$	Neither	Muscle	Liver	Both

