7.5.3 Biomarkers & LC-FAOD Laboratory Measures

A panel of biomarkers will be assessed as clinical indicators of skeletal myopathy and hepatic disease. CK is a useful marker in the investigation of skeletal muscle disease. The presence of CK suggests that muscle cells somewhere in the patient are sufficiently energy deficient to over-contract and rupture, providing an ongoing chronic or non-acute total CK release. Chronic elevations of CK have been reported to indicate patients at risk for major rhabdomyolysis events, although no quantitative relationship has been established yet.

Assessing glucose levels is central to the management of hypoglycemia associated with LC-FAOD. Samples for fasting serum glucose (as tolerated) will be collected on arrival to the clinic; the length of fast, the date and time of the last dose of study medication, and time of collection will be recorded on the CRF. Relevant liver enzymes, including alanine aminotransferase (ALT), aspartate transaminase (AST), and gamma glutamyl transpeptidase (GGT) will be evaluated as indicators of liver injury related to LC-FAOD.

Biomarkers and relevant indicators of LC-FAOD are summarized in Table 7.5.3.1. Blood samples will be collected at each clinic visit to assess relevant biomarkers and laboratory measures of LC-FAOD. For each sample collection, the duration of fasting and time elapsed since last study drug administration will be recorded on the CRF. Where possible, assessment of certain parameters (i.e. glucose, ALT, AST, GGT) will be performed as part of the routine clinical laboratory test panel to avoid unnecessary duplication of testing (see Section 7.5.5.5). Refer to the Study Reference Manual for additional details.

Table 7.5.3.1: Biomarkers and LC-FAOD-related Laboratory Measures

Biomarkers of UX007 Effects	LC-FAOD Laboratory Measures
Skeletal myopathy biomarkers: serum creatine kinase (CK)	Total and free plasma carnitine
Hepatic disease biomarkers: serum glucose, serum liver enzymes (ALT, AST, GGT)	Plasma acylcarnitines Urine organic acids

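### SAP Table 8.7.3 leaves an ALT or AST rise of any size unflagged when CK is at or below ULN and GGT is at or below 1.5 × ULN

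*SAP*

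**What the plan says.** SAP Section 8.7.2.2 introduces the screen in these words: "Potential liver / muscle damage will be assessed based on clinical laboratory test results (and to differentiate it from possible muscle degradation". It works "based on AST, ALT, GGT and CK test results shown below", so bilirubin and alkaline phosphatase play no part. All results are to be listed, and "subjects identified with potential toxicity stemming from liver, muscle or both will be flagged".

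Table 8.7.3 has two rows. If ALT and AST are both at or below 1.5 × ULN, every cell is 'No Toxicity Flag'. If either exceeds 1.5 × ULN, the four cells read "Neither Muscle Liver Both". In order, these are:

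- GGT ≤ 1.5 × ULN with CK ≤ ULN
- GGT ≤ 1.5 × ULN with CK > ULN
- GGT > 1.5 × ULN with CK ≤ ULN
- GGT > 1.5 × ULN with CK > ULN

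The SAP does not define 'Neither', say how it differs from 'No Toxicity Flag', or provide any review for it.

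Elsewhere the documents treat the transaminases as liver markers. Protocol Section 7.5.3 says that ALT, AST and GGT "will be evaluated as indicators of liver injury related to LC-FAOD". SAP Table 8.7.1 lists all three as hepatic disease biomarkers.

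**The concern.** The screen exists to say where a transaminase rise comes from. In the 'Neither' cell the rise has already passed the table's entry threshold, and the table's own CK criterion has ruled out the 'Muscle' label. The marker still abnormal is one that both documents list as hepatic. Yet the subject leaves the screen with no attribution and no flag, because GGT is not raised as well. In effect GGT becomes a precondition for counting ALT or AST as a liver signal, a condition that neither Protocol Section 7.5.3 nor SAP Table 8.7.1 states.

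At stake is how liver safety reads in a study that doses subjects from 6 months of age for up to 7 years without a formal data monitoring committee (SAP Section 3.8). A reader of the flagged list could take the absence of a liver flag as reassurance when the rule could not have produced one.

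**Working it through.** There is no planned figure to reproduce. The check is to run the rule as written and set it beside the SAP's other liver outputs.

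**Inputs, in multiples of ULN**

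- Screen (Table 8.7.3): entry if ALT or AST > 1.5; GGT cut 1.5; CK cut 1.
- CTCAE grade for ALT and AST (Table 11.2.1): Grade 1 above 1 to 3; Grade 2 above 3 to 5; Grade 3 above 5 to 20; Grade 4 above 20.
- Hy's Law (Section 8.7.2.2): bilirubin > 2 and ALT or AST > 3, both required.

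**Rule**

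1. ALT ≤ 1.5 and AST ≤ 1.5: 'No Toxicity Flag'.
2. Otherwise, GGT ≤ 1.5: 'Neither' if CK ≤ 1, 'Muscle' if CK > 1.
3. Otherwise, GGT > 1.5: 'Liver' if CK ≤ 1, 'Both' if CK > 1.

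**Results, with AST at 1 × ULN**

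| ALT | CTCAE grade | GGT 1.5, CK 1 | GGT 1, CK 1.01 | GGT 1.6, CK 1 | Hy's Law, bilirubin 1 | Hy's Law, bilirubin 2.1 |
|---|---|---|---|---|---|---|
| 1.4 | 1 | No Toxicity Flag | No Toxicity Flag | No Toxicity Flag | negative | negative |
| 1.6 | 1 | Neither | Muscle | Liver | negative | negative |
| 3.1 | 2 | Neither | Muscle | Liver | negative | positive |
| 5.1 | 3 | Neither | Muscle | Liver | negative | positive |
| 10 | 3 | Neither | Muscle | Liver | negative | positive |
| 20.1 | 4 | Neither | Muscle | Liver | negative | positive |
| 50 | 4 | Neither | Muscle | Liver | negative | positive |

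The third column never changes once ALT passes 1.5 × ULN. A wider grid (ALT up to 100, AST up to 30, GGT from 0.2 to 1.5) gives only 'Neither' when CK ≤ ULN, and only 'Neither' or 'Muscle' when CK is free to vary. The ordering is also inverted: ALT 50 with GGT 1.5 and CK 1 is unflagged, while ALT 1.6 with GGT 1.6 and CK 1 is 'Liver'.

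**What the other outputs show for the same subject**

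| Output | Shows the rise? | Attributes it to liver or muscle? |
|---|---|---|
| ALT/AST shift tables by worst grade (SAP 8.7.2.1) | Yes, whatever the GGT or CK | No |
| Counts of abnormal results (SAP 8.7.2.2) | Yes | No |
| Listing of all screen results (SAP 8.7.2.2) | Yes, without a flag | No |
| Hepatobiliary adverse event search (SAP 11.3) | Only if reported as an adverse event | No |
| Hy's Law (SAP 8.7.2.2) | Only if bilirubin > 2 × ULN | No |

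Among the outputs described in the SAP, Table 8.7.3 is thus the only one that attributes a rise. Section 9 leaves the full list of tables to a separate document.

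**The case against.** The strongest reply is that this is a descriptive flag in a listing. No endpoint, test or stopping rule depends on it, and the underlying values are reported elsewhere. "Shift tables pairing each subject's baseline severity grade with the subject's highest post-baseline severity grade will be presented", and ALT and AST are among the parameters covered. Protocol Section 7.5.5.7 has clinically significant laboratory changes recorded as adverse events where appropriate, which feeds the hepatobiliary search. A reader might infer that the signal drops out of the safety analysis; the documents do not support that. What remains is narrower: those outputs show the rise without saying whether it comes from liver or muscle.

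A second reply is that asking for GGT corroboration is a reasonable specificity choice where transaminases may come from muscle. Protocol Section 7.5.3 lists the three enzymes together and does not say that each suffices alone. A normal CK does not prove a hepatic source either; the SAP does not say whether the four results must come from the same sample. This stands as an argument against labelling the cell 'Liver'. It does not justify leaving the cell unflagged, because in that cell the table offers no muscle explanation to be specific about.

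Third, 'Neither' is a different label from 'No Toxicity Flag', so these subjects can be found in the listing. That is true, but the SAP gives the label no meaning and no follow-up.

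Two further inferences are tempting. One is that a definable share of liver signals goes unflagged. The documents give no distribution of GGT or CK among such subjects, and those with GGT ≤ 1.5 × ULN and CK > ULN are flagged, as 'Muscle'. The other is that the 'Muscle' cell should be relabelled once ALT or AST exceeds 3 × ULN. The SAP uses that cut only jointly with bilirubin, so it gives no support for a stand-alone rule.

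**Conclusion.** The point holds for the screen itself. In Table 8.7.3, ALT or AST above 1.5 × ULN with CK ≤ ULN and GGT ≤ 1.5 × ULN is always 'Neither' and never flagged, up to and including Grade 4. This follows from the printed cells and rests on no clinical or numerical assumption. It does assume that 'Neither' is outside the flagged categories, which is the plain reading of the sentence on flagging.

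How many subjects fall in the cell cannot be derived from the documents. Protocol Section 7.5.3 describes chronic CK elevation in this disease, which would move some of them to 'Muscle'. There they are flagged, but a high-grade ALT or AST rise is not distinguished from a minor one.

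The consequence is a gap in attribution, not a lost signal. It is worth correcting because it sits in the one described output whose purpose is attribution, and the correction is small.

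**What to change.** In SAP Table 8.7.3, rename the 'Neither' cell 'Liver not excluded' and add that category to those the text says will be flagged. Beside each flag in the listing, print the subject's ALT and AST grades from Table 11.2.1, so that high-grade rises in the 'Muscle' cell can also be seen. Leave the other cells and all thresholds as they are.

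The change needs one relabelled cell, one amended sentence and the grades added to the listing, using data already collected. The drawback is a few more flagged subjects to review, some of whose rises will turn out not to be hepatic. The proposed label allows for that, since it asserts no cause.
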